9.4.6.5. Columbia Suicide-Severity Rating Scale

Suicide-related thoughts and behaviors occurring during treatment will be summarized based on responses to the C-SSRS consistent with the C-SSRS Scoring and Data Analysis Guide (CSSRS [WWW]).

9.4.7. Subgroup Analyses

Subgroup analyses will be conducted for the primary efficacy measure of NRS average pain. The subgroup analyses will be provided for the following subgroups using data from the respective ISA only:

- baseline pain severity: baseline pain severity category (moderate vs severe) defined by baseline NRS average pain <7 versus baseline NRS average pain ≥ 7
- gender, and
- pooled investigative site.

For the subgroups of baseline pain severity and gender, the Bayesian MMRM method described in Section 9.4.2 will be utilized, with the relevant terms added for subgroup, subgroup-by-treatment, subgroup-by-time interval without the baseline, and subgroup-by-treatment-by time interval interactions without the baseline. For the pooled investigative site subgroup analysis, the change from baseline to endpoint will be evaluated using a Bayesian model with terms for pooled investigative site, baseline pain severity, and treatment-by-pooled investigative site interaction.

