9.1. Statistical Hypotheses

For each ISA in this master protocol, a Bayesian critical success factor (CSF) will be defined in the ISA and used to evaluate whether the ISA met its primary endpoint. The CSF will be evaluated for the primary efficacy endpoint, average pain intensity as measured by the NRS, using the methodology described in Section 9.4.2 and will be calculated at the conclusion of the double-blind portion of each ISA within the master protocol.

The CSF will have the general form of:

- probability (treatment effect < effect of interest) > probability threshold.

The treatment effect will be defined as the LY estimate–placebo estimate of the change from baseline at endpoint. The effect of interest is typically found through a literature search or clinical judgement. The probability threshold is generally set to have a desired level of confidence in the treatment effect or to have the desired operating characteristics under a range of plausible, assumed drug effect scenarios of truth, including a null effect.

Additional hypotheses will include the comparison of each active intervention with placebo for the prespecified objectives and endpoints defined in Section 3.

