9.4.1.1. Missing Data

The NRS value of average pain and worst pain over the past 24 hours will be collected daily for each participant. For the statistical analyses, the average NRS value of the average and worst pain over the past 24 hours will be calculated for both weekly intervals and biweekly intervals.

The average of the weekly intervals for the NRS will result in 8 postbaseline observations, and the average of the biweekly intervals will result in 4 postbaseline observations for each participant if a participant completes the placebo-controlled portion of the study.

The average of the weekly intervals for the NRS will be used in the primary efficacy analysis and other analyses described below, unless otherwise specified in the SAP.

A participant must have 50% or greater of the daily NRS values during the prespecified time interval to calculate the average NRS value; otherwise, the average NRS value for that visit will be considered missing.

Missing data for other variables and analyses will be described in the master protocol SAP.

For all Bayesian analyses, the missing values will be accounted for naturally using the Bayesian imputation of missing values.

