9.4.2. Primary Endpoint and Analysis

The primary efficacy measure will be the same across all disease states and ISAs.

The primary efficacy analysis for an ISA will be conducted when all participants randomized to the ISA have completed the placebo-controlled portion of the ISA. The follow-up period may vary by ISA. Therefore, the primary efficacy analysis may be conducted prior to conclusion of the ISA and the collection of all follow-up data.

The primary efficacy analysis will be performed using a Bayesian MMRM method where the baseline information is modeled as a dependent variable. The baseline estimated means will be constrained to be the same between treatment groups due to randomization (Liang and Zeger, 2000). The primary efficacy analysis of the ISA of interest will be conducted on either the modified intention to treat (mITT) population or enhanced ITT population (see Section 9.3). The enhanced ITT population includes participant level data from ongoing ISAs and/or ISAs that have completed. Participants from ongoing ISAs must have had the opportunity to complete the placebo-controlled portion of the ISA to be included in the primary efficacy analysis for the ISA of interest. The ISA SAP will define the exact participant population included in the primary efficacy analysis.

The Bayesian CSF for the primary efficacy analysis will be defined in the ISA SAP for each respective ISA. The 95% credible intervals will be provided for the key parameters of interest.

This table describes information related to the primary efficacy measure.

Primary Efficacy Measure	Mean change from baseline to endpoint for average pain intensity as measured by the NRS. The exact endpoint for each ISA will be defined in the ISA SAP and may be defined, for example, as the last time point, the average of the last 2 time points, etc.
Data Collection	The NRS average pain will be collected daily. Average scores will be calculated over weekly and biweekly time intervals and will be available for analysis. The average of the weekly time-interval will be used for the primary efficacy analysis.
Primary Analysis	Efficacy of the active treatment(s) compared with placebo
Analysis Method	Bayesian MMRM analysis
Outcome Variable	The raw baseline and postbaseline values will be included in the response vector when fitting the statistical model. The change from baseline will be assessed via the statistical model.

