Fixed Categorical Effects in Model	
 • Time interval • Interaction of treatment by time interval without the baseline • Average baseline pain severity category (moderate or mild vs severe), defined by baseline NRS <7 vs baseline NRS ≥7 • Pooled investigative site
Additional Covariates in Model	Any stratification variable used for randomization of the ISA of interest will also be included in the model. Additional covariates may also be specified at an ISA level.

Abbreviations: ISA = intervention-specific appendix; MMRM = mixed-model repeated measures; NRS = numeric rating scale; SAP = statistical analysis plan.

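### The subgroup model in Section 9.4.7 adds a subgroup-by-treatment term not limited to postbaseline intervals, which contradicts the equal-baseline constraint of the Section 9.4.2 model it extends

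*Protocol*

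**What the plan says.** Protocol Section 9.4.2 defines the primary model with baseline as part of the outcome: "The raw baseline and postbaseline values will be included in the response vector when fitting the statistical model". It then states: "The baseline estimated means will be constrained to be the same between treatment groups due to randomization". The table of model effects is consistent with this. Treatment has no main effect and appears only as "Interaction of treatment by time interval without the baseline".

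Section 9.4.7 applies that same model to two of its subgroup factors, severity and gender, and extends it. The list of additions opens with these words: "with the relevant terms added for subgroup, subgroup-by-treatment, subgroup-by-time interval without the baseline". The last item on the list is the three-way term, worded as "subgroup-by-treatment-by time interval interactions without the baseline". Four terms are therefore added. Both interactions involving time are limited to postbaseline intervals. The subgroup-by-treatment interaction is not.

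Section 9.1 gives the scale of the effect: "The treatment effect will be defined as the LY estimate–placebo estimate of the change from baseline at endpoint".

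**The concern.** In a model with baseline in the response vector, a subgroup-by-treatment term with no time limit acts on every response, including baseline. It allows the arms to differ at baseline within a subgroup, which Section 9.4.2 rules out by design. The constraint is what gives the treatment contrast its baseline adjustment. Without it, the contrast in change from baseline becomes the plain difference in mean change scores.

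What is at stake is the precision of the subgroup effects, and a model that depends on an unstated software choice. This is master-protocol text, so every ISA that follows it inherits the wording.

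**Working it through.** The protocol states no figure on this point, so there is nothing to reproduce. The check asks what the extra term does to the model and then what it does to the standard error (SE).

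**Inputs from the protocol.** The model terms are those in Sections 9.4.2 and 9.4.7. The response has a baseline value plus weekly averages (Section 9.4.1.1: "The average of the weekly intervals for the NRS will result in 8 postbaseline observations"). There are two levels per subgroup factor.

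**Assumed, because the protocol gives no values.** One active arm against placebo, 1:1 allocation, complete data and flat priors. SDs, correlations and coding are varied as shown. The SE ratios do not depend on total sample size.

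**Step 1: what the term adds.** Treatment by postbaseline time plus subgroup by treatment by postbaseline time already give each subgroup its own treatment effect at each of the 8 weeks. An unrestricted subgroup-by-treatment term can therefore add only treatment differences at baseline. How many depends on the coding:

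| Coding | Extra parameters | Baseline constraint |
|---|---|---|
| Reference-dummy product | 1 | Kept in the reference subgroup, fully released in the other |
| Class/cell | 2 | Fully released in both |
| Effect (+1/-1) | 1 | Partly released in both (equal and opposite baseline differences) |

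A standard formula parser, given these terms without a treatment main effect, produces the class/cell version. The rank of the design goes from 10 to 12 in a reduced check, and the baseline difference becomes free in both subgroups.

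**Step 2: formula where the constraint is fully released.** Let Vb and Vy be the variances at baseline and week 8, and C their covariance. With n per arm in the subgroup:

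- Constrained: variance = (2/n)(Vy - C²/Vb)
- Released (change score): variance = (2/n)(Vb + Vy - 2C)
- Excess = (2/n) × Vb(1 - C/Vb)², which is never negative
- SE ratio = sqrt[(Vb + Vy - 2C)/(Vy - C²/Vb)]

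With equal SDs and correlation r, this is sqrt[2(1 - r)/(1 - r²)] = sqrt[2/(1 + r)].

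**Step 3: equal SDs, compound symmetry, 50/50 subgroup split.** Exact generalised least squares on all nine time points gives the same values as the formula:

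| r | Fully released subgroup | Each subgroup, effect coding |
|---|---|---|
| 0.3 | sqrt(2/1.3) = 1.240 | 1.127 |
| 0.5 | sqrt(2/1.5) = 1.155 | 1.080 |
| 0.7 | sqrt(2/1.7) = 1.085 | 1.043 |
| 0.9 | sqrt(2/1.9) = 1.026 | 1.013 |

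Under reference coding the reference subgroup stays at 1.000. Without the term, both subgroups are at 1.000 and the baseline difference is exactly 0.

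**Step 4: upper end.** Under AR(1) with adjacent-week correlation 0.3 to 0.9, the baseline-to-week-8 correlation is 0.3⁸ ≈ 0.000 to 0.9⁸ = 0.430. The ratio runs from sqrt(2/1.000) = 1.414 to sqrt(2/1.430) = 1.182.

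**Step 5: lower end, severity subgroups.** Cutting on baseline NRS at 7 reduces the baseline variance within each subgroup. Assume baseline mean 6.5, baseline SD 1.2 and week-8 SD 2. The variance within subgroup is then about 0.67 (moderate) and 0.37 (severe). The slope C/Vb = r × 2/1.2 is 0.50, 0.83 and 1.17 at r = 0.3, 0.5 and 0.7, where r is the correlation before the cut. For the moderate group at r = 0.3, the excess is 0.67 × (1 - 0.50)² = 0.17. The residual variance is 4 × (1 - 0.09) = 3.64, so the ratio is sqrt(1 + 0.17/3.64) = 1.023. Across both groups and the three correlations the ratios are 1.002 to 1.023.

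**The case against.** The strongest reply is that Section 9.4.7 invokes the Section 9.4.2 method as a whole, and the equal-baseline constraint defines that method. The list of added terms reads as shorthand: it adds a subgroup main effect even for severity, which is already a fixed effect in Section 9.4.2. An implementer could keep the constraint and apply the term only after baseline. Section 9.4.2.1 also leaves the exact model specification to the ISA SAP, and coding and priors belong there.

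Part of this stands. A careful programmer may well arrive at the intended model, and informative priors could shrink the effect. But Section 9.4.7 itself names the terms and writes the baseline limit on two of them, so its absence on the third is hard to read as implied. Followed literally, the list conflicts with Section 9.4.2.

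A reader might go further and infer that the constraint breaks in one subgroup only, so that the two subgroup effects are on unequal footing and their contrast depends on the reference level. The protocol does not support this. It states no coding. The asymmetry follows only from reference-dummy coding, while class/cell and effect coding affect both subgroups. Nor does the protocol supply the SDs and correlations needed to fix a single figure for the precision loss.

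**Conclusion.** The inconsistency is real but minor. As written, the unrestricted term contradicts the model it is added to, contributes nothing after baseline, and can only leave the subgroup standard errors unchanged or make them larger under flat priors. Where the constraint is fully released, the increase is about 3% to 24% under equal SDs, compound symmetry and r from 0.9 to 0.3. It is up to about 41% with almost no baseline-to-endpoint correlation, and about 0% to 2% in the truncated severity example. The gender subgroups, where baseline is not truncated, are therefore the more exposed. All these figures rest on assumed inputs.

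No bias has been shown: with randomised arms, the concern about the change-score contrast is its precision. The primary analysis and the critical success factor do not use this term and are unaffected.

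**What to change.** In Section 9.4.7, either delete subgroup-by-treatment from the list of added terms, or attach the same postbaseline limit that the two time interactions carry. State that the equal-baseline constraint of Section 9.4.2 holds within each subgroup.

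Either edit changes a few words, loses no postbaseline flexibility and removes the dependence on coding. If an ISA uses informative priors, it may prefer to keep a postbaseline-limited two-way term, because the split between two-way and three-way terms then affects shrinkage. That choice can be recorded with the priors in the ISA SAP.

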9.4.8. Sensitivity Analysis

Sensitivity analyses of the primary efficacy analysis will be conducted to evaluate the impact of the borrowing of placebo and treatment-effect information, as well as the impact of missing data.

A tipping point analysis will also be conducted to evaluate the impact of missing data for the primary efficacy analysis.

The details of the sensitivity analyses will be provided in the ISA SAP.

9.5. Interim Analyses

The master protocol will not require or specify interim analyses for a specific ISA. If an interim analysis is planned for an ISA, the details (for example, timing, rationale, use of participants in other ISAs) will be provided in the ISA or ISA SAP. The potential reasons for interim analyses could include futility analyses, early efficacy analyses, safety analyses, or other analyses needed for key business decisions and planning.

Unblinding details will be specified in the unblinding plan section of the respective ISA SAP or in a separate unblinding plan document.

9.6. Data Monitoring Committee

The AC will provide oversight for safety by reviewing unblinded data for each ISA. The structure and the responsibilities of the AC will be detailed in the AC charter.

Safety analyses for review will be detailed in each ISA SAP and in the AC charter.

The AC may evaluate additional objectives that are specific to an individual ISA, for example, assessing futility or early efficacy. If this is requested, details will be specified in the AC charter.

The committees that will be established to support the master protocol and ISA teams are described in Appendix 1, Section [10.1.5](#).

10. Supporting Documentation and Operational Considerations

10.1. Appendix 1: Regulatory, Ethical, and Study Oversight Considerations

10.1.1. Regulatory and Ethical Considerations

- This study will be conducted in accordance with the protocol and with the following:
 - consensus ethical principles derived from international guidelines including the Declaration of Helsinki and Council for International Organizations of Medical Sciences (CIOMS) International Ethical Guidelines
 - applicable International Council for Harmonisation (ICH) good clinical practice (GCP) guidelines, and
 - applicable laws and regulations.
- The protocol, protocol amendments, informed consent form (ICF), Investigator Brochure, and other relevant documents (for example, advertisements) must be submitted to an ERB by the investigator and reviewed and approved by the ERB before the study is initiated.
- Any amendments to the protocol will require ERB approval before implementation of changes made to the study design, except for changes necessary to eliminate an immediate hazard to study participants.
- The investigator will be responsible for the following:
 - providing written summaries of the status of the study to the ERB annually or more frequently in accordance with the requirements, policies, and procedures established by the ERB
 - notifying the ERB of SAEs or other significant safety findings as required by ERB procedures, and
 - providing oversight of study conduct for participants under their responsibility and adherence to requirements of 21 CFR, ICH guidelines, the ERB, European regulation 536/2014 for clinical studies (if applicable), and all other applicable local regulations.

10.1.2. Financial Disclosure

Investigators and subinvestigators will provide the sponsor with sufficient, accurate financial information as requested to allow the sponsor to submit complete and accurate financial certification or disclosure statements to the appropriate regulatory authorities. Investigators are responsible for providing information on financial interests for the master protocol and each ISA in which the investigator participates and for 1 year after completion.

10.1.3. Informed Consent Process

- The investigator or his/her representative will explain the nature of the study, including the risks and benefits, to the participant or his/her legally authorized representative and answer all questions regarding the master protocol and eligible ISAs.

- Participants must be informed that their participation is voluntary. Participants or their legally authorized representative will be required to sign a statement of informed consent that meets the requirements of 21 CFR 50, local regulations, ICH guidelines, Health Insurance Portability and Accountability Act (HIPAA) requirements, where applicable, and the ERB or study center.
- The medical record must include a statement that written informed consent was obtained before the participant was entered in the master protocol and ISA, and the date the written consent was obtained. The authorized person obtaining the informed consent must also sign the ICF.
- Participants must be re-consented to the most current version of the ICF(s) during their participation in the study.
- A copy of the ICF(s) must be provided to the participant or the participant's legally authorized representative and is kept on file.

Participants who are rescreened are required to sign a new ICF.

10.1.4. Data Protection

Participants will be assigned a unique identifier by the sponsor. Any participant records, datasets, or biological samples that are transferred to the sponsor will contain the identifier only; participant names or any information which would make the participant identifiable will not be transferred.

The participant must be informed that his/her personal study-related data will be used by the sponsor in accordance with local data protection law. The level of disclosure must also be explained to the participant who will be required to give consent for their data to be used as described in the ICF.

The participant must be informed that his/her medical records may be examined by Clinical Quality Assurance auditors or other authorized personnel appointed by the sponsor, by appropriate IRB/IEC members, and by inspectors from regulatory authorities.

10.1.5. Committees Structure

These committees will be established to support the master protocol and ISA teams:

- Assessment Committee (AC), and
- Internal Steering Committee, including a Statistical Analysis Subcommittee (SASC).

The AC will routinely (for example, quarterly) evaluate safety for all ISAs within the master protocol. The safety reports will be provided for an ISA only and, as appropriate, for the aggregate data of an intervention if it is studied in multiple disease states.

The Internal Steering Committee will be established to support the strategic and technical integration of the master protocol to achieve Lilly's overarching clinical development needs.

The Internal Steering Committee will function as a resource group to provide oversight of the master protocol including consultation, advice, analysis, and feedback to clinical teams and other

interested parties during the study. It will be composed of cross-functional representatives from departments such as medical, statistics, clinical operations, and project management.

The SASC will be a small cross-functional group that will function as an expert panel for consultation, advice, and feedback to the Internal Steering Committee and the ISA teams. One of the primary roles of the SASC is to generate the master protocol level integrated datasets, which include data from completed and ongoing ISAs. Thus, the SASC will be unblinded to data from both ongoing and completed ISAs. The SASC will

- provide the AC with unblinded safety reports,
- be responsible for communication with the AC, and
- generate analysis reports for ongoing or completed ISAs based on the integrated datasets..

10.1.6. Dissemination of Clinical Study Data

A clinical study report will be provided for each ISA.

10.1.7. Data Quality Assurance

All participant data relating to the study will be recorded on a printed or electronic case report form (CRF), unless transmitted to the sponsor or designee electronically (for example, laboratory data). The investigator is responsible for verifying that data entries are accurate and correct by physically or electronically signing the CRF.

The investigator must maintain accurate documentation (source data) that supports the information entered in the CRF.

The investigator must permit study-related monitoring, audits, ERB review, and regulatory agency inspections and provide direct access to source data documents.

Monitoring details describing strategy (for example, risk-based initiatives in operations and quality such as Risk Management and Mitigation Strategies and Analytical Risk-Based Monitoring), methods, responsibilities and requirements, including handling of noncompliance issues and monitoring techniques, are provided in the Monitoring Plan.

The sponsor or designee is responsible for the data management of this study, including quality checking of the data.

The sponsor assumes accountability for actions delegated to other individuals (for example, contract research organizations).

Study monitors will perform ongoing source data verification to confirm that data entered into the CRF by authorized study personnel are accurate, complete, and verifiable from source documents; that the safety and rights of participants are being protected; and that the study is being conducted in accordance with the currently approved protocol and any other study agreements, ICH GCP, and all applicable regulatory requirements.

Records and documents, including signed ICFs, pertaining to the conduct of this study and each ISA must be retained by the investigator for 15 years after study completion, unless local regulations or institutional policies require a longer retention period. No records may be destroyed during the retention period without the written approval of the sponsor. No records may be transferred to another location or party without written notification to the sponsor.

In addition, the sponsor or its representatives will periodically check a sample of the participant data recorded against source documents at the study site. The study may be audited by the sponsor or its representatives and/or regulatory agencies at any time. Investigators will be given notice before an audit occurs.

Data Capture System

The investigator is responsible for ensuring the accuracy, completeness, legibility, and timeliness of the data reported to the sponsor.

An electronic data capture (EDC) system will be used in this study for the collection of CRF data. The investigator maintains a separate source for the data entered by the investigator or designee into the sponsor-provided EDC system. The investigator is responsible for the identification of any data to be considered source and for the confirmation that data reported are accurate and complete by signing the CRF.

Additionally, electronic clinical outcome assessment (eCOA) data (participant-focused outcome instrument) will be directly recorded by the participant into a provisioned hand-held device. The eCOA data will serve as the source documentation, and the investigator does not maintain a separate written or electronic record of these data. Authorized study personnel will monitor participant compliance with eCOA entry and re-educate participants on the importance of compliance as necessary. Some eCOA data values may be blinded to the site during the study to minimize any potential rating bias.

CCI

Data collected via the sponsor-provided data capture systems will be stored at a vendor selected by the sponsor. The investigator will have continuous access to the unblinded data during the study and until decommissioning of the data capture systems. Prior to decommissioning, the investigator will receive an archival copy of all eCOA data for retention.

Data managed by a central vendor, such as laboratory test data, will be stored electronically in the central vendor's database system, and reports will be provided to the investigator for review and retention. Data will subsequently be transferred from the central vendor to the sponsor data warehouse.

Data from complaint forms submitted to the sponsor will be encoded and stored in the global product complaint management system.

